### **3.3 Inclusion of Women and Minorities**

Men and women of all races and ethnicities who meet the above-described eligibility criteria are eligible to participate in this study.

Based on WFBCCC population estimates, we expect approximately 30% of participants to be women. Similarly, we expect approximately 1% of study participants to be Hispanic/Latino. We plan to enroll at least 15% Black or African American. Should we not meet or exceed these estimates, the PI will engage the Cancer Center Health Equity Advisory Group to discuss strategies to enhance recruitment in these target populations.

Quad-Shot Radiotherapy in Combination with Immune Checkpoint Inhibition for  
Advanced/Recurrent Head and Neck Cancer  
Wake Forest Baptist Comprehensive Cancer Center  
WFBCCC60320

## 4.0 Methods

### 4.1 Registration Procedure

All patients entered on any WFBCCC trial, whether treatment, companion, or cancer control trial, **must** be linked to the study in EPIC within 24 hours of Informed Consent. Patients **must** be registered prior to the initiation of treatment.

You must perform the following steps in order to ensure prompt registration of your patient:

1. Complete the Eligibility Checklist (Appendix A)
2. Complete the Protocol Registration Form (Appendix B)
3. Alert the Cancer Center registrar by phone, *and then* send the signed Informed Consent Form, Eligibility Checklist and Protocol Registration Form to the registrar, either by fax or e-mail.

\*Protocol Registration is open from 8:30 AM - 4:00 PM, Monday-Friday.

4. Fax/e-mail ALL eligibility source documents with registration. Patients **will not** be registered without all required supporting documents.

Note: If labs were performed at an outside institution, provide a printout of the results. Ensure that the most recent lab values are sent.

To complete the registration process, the Registrar will:

- assign a patient study number
- register the patient on the study

### 4.2 Study Design

This is a single-arm, non-randomized pilot study to evaluate the efficacy and tolerability of combination of **two standard of care interventions** (quad-shot palliative radiotherapy and pembrolizumab immunotherapy) for patients with advanced/recurrent/metastatic head and neck cancer.

Fifteen patients will be enrolled who have no curative localized treatment options, are eligible for palliative immunotherapy (pembrolizumab), have a lesion that can be targeted by radiotherapy, and are eligible for palliative radiotherapy as recommended by their radiation oncologist.

Quad-Shot Radiotherapy in Combination with Immune Checkpoint Inhibition for  
Advanced/Recurrent Head and Neck Cancer  
Wake Forest Baptist Comprehensive Cancer Center  
WFBCCC60320

Patients eligible for this study will be those scheduled to receive palliative immunotherapy with the immune checkpoint inhibitor pembrolizumab (which is standard of care) for advanced, R/M head and neck SCC according to standard of care practice. They will also be eligible for palliative quad-shot radiotherapy according to the standard of care for advanced/recurrent/metastatic HSNCC. Quad-shot radiotherapy will be applied between immunotherapy cycle 2-3 or between immunotherapy cycle 3-4, within the last week of the cycle, and not to be delivered on the same day as ICI administration. Up to two additional quad-shot cycles will be delivered between cycles 6-7 or 7-8 (prior to cycle 8) and 11-12 or 12-13 (prior to cycle 13) of immunotherapy. The additional quad-shot treatments will be delivered in a similar fashion, in the last week of the ICI cycle.

Restaging imaging with CT, MRI or PET/CT will be obtained every 5-6 immunotherapy treatments. For the purposes of lesion measurements, follow-up imaging must be performed using the same modality (CT or MRI) as was used for initial baseline imaging. PET/CT may be utilized for follow-up imaging at the clinician's discretion. The maximum response in the targeted lesion and in the non-targeted lesions will be assessed. Subsequent immunotherapy cycles will be delivered after quad-shot radiotherapy until tumor progression or treatment intolerance.

Palliative local (non-systemic) interventions to other sites that are not quad-shot radiotherapy target sites is allowable while on study protocol treatment for the management of cancer symptoms. This should not be utilized for progression of disease at that site.

The study treatment portion ends for all patients with the last administration of the immunotherapy.

We will monitor and document clinical toxicity per NCI Common Terminology Criteria for Adverse Events version 5.0 during the treatment and for two additional visits 30 days apart from the end of treatment with immunotherapy. Subjects who decline to return to the site for evaluations will be offered follow-up by phone up to 2 months as an alternative and the PI will make every effort to collect toxicity data from medical records.

Patients will be subsequently followed for progression-free survival and overall survival outcomes. Subsequent visits can be accomplished in person or over the phone and clinical and imaging data will be collected from medical records as available.

Patient-reported outcomes will be obtained at each time point using a tailored checklist of PRO-CTCAE head and neck cancer-specific items.

Saliva and blood for correlative studies will be collected before each treatment with immunotherapy for the first 5 administrations and before the quad-shot administration. Saliva and blood samples will only need to be collected on the first day of Quadshot treatment. In the cases in which the patients will receive a 2nd quad-shot and possibly a third quad-shot, blood and saliva will be collected before the respective radiation treatments as well as before the immunotherapy cycles that proceed and follow the quad-shot treatments.

PD-L1 receptors will be tested in all patients as per standard of care. Next generation sequencing is encouraged and will be done whenever possible from the blood or tumor if available.

Quad-Shot Radiotherapy in Combination with Immune Checkpoint Inhibition for  
Advanced/Recurrent Head and Neck Cancer  
Wake Forest Baptist Comprehensive Cancer Center  
WFBCCC60320

If any patient does not complete the study treatment and investigations, the patient will be replaced.

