#### 4.3.6 Radiotherapy Timing:

Quad-Shot Radiotherapy in Combination with Immune Checkpoint Inhibition for  
Advanced/Recurrent Head and Neck Cancer  
Wake Forest Baptist Comprehensive Cancer Center  
WFBCCC60320

- Radiation Therapy will be given as outlined in the Study Schema and according to the Study Calendar in Section 6.1:
  - Quad-shot Cycle #1: prior to cycle 4 (between pembrolizumab cycle 2-3 or 3-4) for all patients
  - Quad-shot Cycle #2 (if delivered): prior to cycle 8 (between pembrolizumab cycles 6-7 or 7-8)
  - Quad-shot Cycle #3 (if delivered): prior to cycle 13 (between pembrolizumab cycles 11-12 or 12-13).
- Radiotherapy is **NOT** to be given on the same day as immunotherapy/ICI infusion.
- Outside of this restriction, the timing of the delivery of 4 radiotherapy fractions that make up each cycle is not required.
- Though specific days are not mandated, it is **strongly recommended** that at least 1 day of the two consecutive days (including 2 of the 4 planned RT fractions per cycle) falls within 7 days prior to the delivery of an immunotherapy infusion.

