### 4.4.2 Pembrolizumab Doses and treatment regimens

Pembrolizumab 200 mg will be given every 3 weeks to tumor progression or treatment tolerance.

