- c. With first administration of pembrolizumab only and then as clinically indicated. Subjects will have their blood pressure and pulse measured before, during and after the infusion at the following times (based on a 60-minute infusion):
  - At the beginning of the infusion (at 0 minutes)
  - At 30 minutes during the infusion ( $\pm 5$  minutes)
  - At the end of the infusion (at 60 minutes  $\pm 5$  minutes)
  - In the 1 hour observation period post-infusion: 30 and 60 minutes after the infusion (ie, 90 and 120 minutes from the start of the infusion) ( $\pm 5$  minutes) – for the first infusion only and then for subsequent infusions as clinically indicated
  - If the infusion takes longer than 60 minutes then blood pressure and pulse measurements should be collected every 30 minutes ( $\pm 5$  minutes) and as described above or more frequently if clinically indicated.
- d. ECG during screening and at Day1 –baseline. Thereafter as clinically indicated. Baseline and abnormal ECG at any time in triplicate others single. Triplicate EKG is only needed at screening, and not on Cycle 1 Day 1 unless something clinically significant was seen at screening.
- e. Free T3 and free T4 will only be measured if TSH is abnormal. They should also be measured if there is clinical suspicion of an adverse event related to the endocrine system.
- f. CT (preferred) or MRI scans, preferably with IV contrast, are collected during screening (for baseline) and as close to and prior to initiation of study treatment but not more than 14 days  $\pm$  5 days prior to first treatment. Will then be performed every 5 cycles ( $\pm$  1 cycle) for tumor response measurement
- g. PET scan will be performed in all cases if reimbursed by Medical Insurance or funded. It will be performed as close to the initiation of treatment but not more than 28 days prior to treatment. Will then be performed in follow up as clinically indicated and if approved by medical insurance.

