### **6.5 Duration of Follow Up**

Patients will be followed for a minimum of 2 times every 30 days after the last study drug is administered for adverse events monitoring. Follow-up for serious adverse events and mortality after the last study dose is administered will take place during the routine clinic visits that the patient will have during the 60-day follow-up window (Also referenced in Appendix D). If no visit occurs during this window, a phone call confirmation should be made to the patient to determine vital status and whether any adverse events and in particular, Grade 4 unexpected adverse events occurred during that window of time and recorded on Appendix F.

Patients will be followed according to the treating physician after removal from study or until death, whichever occurs first. Patients removed from study for unacceptable adverse events will be followed until resolution or stabilization of the adverse event.

Patients will be followed until death for monitoring survival study endpoints. Frequency of visits will be established by the treating physician and will be done in person or over the phone. Tumor imaging will be also performed at the discretion of the treating physician and results will be collected from the medical records. Alternatively, if the patient stops visiting with our clinic, tumor status and survival information will be collected by phone from the patient and from any other oncology office.

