### **6.6 Criteria for Removal from Study**

Patients will be removed from study when any of the following criteria apply:

Quad-Shot Radiotherapy in Combination with Immune Checkpoint Inhibition for Advanced/Recurrent Head and Neck Cancer  
Wake Forest Baptist Comprehensive Cancer Center  
WFBCCC60320

- Patient withdrawal of consent or loss to follow-up.
- Adverse event that, in the opinion of the investigator or the sponsor, contraindicates further dosing.
- Subject is determined to have met one or more of the exclusion criteria for study participation at study entry and continuing investigational therapy might constitute a safety risk.
- Pregnancy or intent to become pregnant
- Grade  $\geq 3$  infusion reaction.
- Subject noncompliance that, in the opinion of the investigator or sponsor, warrants withdrawal; eg, refusal to adhere to scheduled visits.
- Initiation of alternative anticancer therapy including another investigational agent.
- Confirmation of PD and investigator determination that the subject is no longer benefiting from protocol treatment.
- Death.

Subjects who are permanently discontinued from further receipt of investigational product, regardless of the reason (withdrawal of consent, due to an AE, other), will be identified as having permanently discontinued treatment.

Subjects who are removed from study prior to completing at least 2 cycles of ICI followed by at least 1 cycle of quad-shot radiotherapy followed by at least 2 cycles of ICI will be discontinued from the study and replaced.

Subjects who are permanently discontinued from receiving investigational product will be followed for safety until follow-up criteria are met in Section 6.4. Subjects who decline to return to the site for evaluations will be offered follow-up by phone for at least 60 days as an alternative.

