## **7.0 Measurement of Effect**

### **7.1 Antitumor Effect – Solid Tumors**

In accordance with the standard of care, after a baseline scans obtained prior to study registration, patients will be reevaluated for response after 5 cycles of immunotherapy. Patients who continue to receive ICI at the discretion of the medical oncologist will be evaluated again after 10 cycles of ICI.

Response and progression will be evaluated in this study using the Response Evaluation Criteria in Solid Tumors (RECIST) criteria 1.1.(40) Changes in the largest diameter

(unidimensional measurement) of the tumor lesions and the shortest diameter in the case of malignant lymph nodes are used in the RECIST criteria.

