### 7.1.1 Definitions

- **Evaluable for toxicity:**

Only those patients who have received at least 1 fraction of radiotherapy and at least 1 cycle of ICI will be evaluable for toxicity from the time of their first fraction of radiotherapy.

- **Evaluable for objective response:**

Only those patients who received at least one cycle of quad-shot radiotherapy (given after at least 2 cycles of ICI), and have had their target disease re-evaluated will be evaluable. These patients will have their response classified according to the definitions stated below.

Note: Per Section 6.6, subjects who are removed from study prior to completing at least 2 cycles of ICI followed by at least 1 cycle of quad-shot radiotherapy followed by at least 2 cycles of ICI will be discontinued from the study and replaced.

- **Evaluable Non-Target Disease Response.**

Patients who have lesions present at baseline that are evaluable but do not meet the definitions of target disease, have received at least one cycle of quad-shot radiotherapy, and have had their disease re-evaluated will be considered evaluable for non-target disease. The response assessment is based on the presence, absence, or unequivocal progression of the lesions.

- **Measurable disease / measurable lesions**

Measurable lesions are defined as those that can be accurately measured in at least one dimension (longest diameter to be recorded) as  $\geq 20$  mm by chest x-ray, as  $\geq 10$  mm with CT scan, or  $\geq 10$  mm with calipers by clinical exam. All tumor measurements must be recorded in millimeters (or decimal fractions of centimeters).

- **Malignant lymph nodes.**

To be considered pathologically enlarged and measurable, a lymph node must be  $\geq 15$  mm in short axis when assessed by CT scan (CT scan slice thickness recommended to be no greater than 5 mm). At baseline and in follow-up, only the short axis will be measured and followed.

- **Non-measurable disease / non-measurable lesions:**

All other lesions (or sites of disease), including small lesions (longest diameter  $<10$  mm or pathological lymph nodes with  $\geq 10$  to  $<15$  mm short axis), are considered non-measurable disease. Bone lesions, leptomeningeal disease, ascites, pleural/pericardial effusions, lymphangitis cutis/pneumonitis, inflammatory breast disease, and abdominal masses (not followed by CT or MRI), are considered as non-measurable.

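### Required response scans follow infusion count only, so a patient who meets the treatment minimum at infusion 4 and then stops may leave the primary ORR unassessed, and the replacement rules conflict on what happens next

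*Combined protocol and SAP*

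**What the plan says.** **When scans are due.** Section 4.2: "Restaging imaging with CT, MRI or PET/CT will be obtained every 5-6 immunotherapy treatments". Section 7.1: "patients will be reevaluated for response after 5 cycles of immunotherapy", and again after 10 cycles if treatment continues. Footnote f to the Study Calendar (6.1), on CT or MRI: "Will then be performed every 5 cycles", with a window of one cycle either way. All three count infusions.

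**After pembrolizumab stops.** The follow-up table in 6.2 has no tumor assessment. Section 6.5 says "Tumor imaging will be also performed at the discretion of the treating physician", with results taken from the records.

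**Who is evaluable.** Section 7.1.1 counts patients for response only if they had at least 2 pembrolizumab cycles and then a quad-shot, and "have had their target disease re-evaluated will be evaluable". Section 11.3 bases the stated precision on 15 patients evaluable in that sense.

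**Who is replaced.** Section 6.6, repeated in a note in 7.1.1, replaces subjects removed before "completing at least 2 cycles of ICI followed by at least 1 cycle of quad-shot radiotherapy followed by at least 2 cycles of ICI". The last sentence of 4.2 is broader: it replaces anyone who does not finish both treatment and investigations.

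**The concern.** The least treatment that keeps a patient in the study under 6.6 can be complete before the infusion that makes the first response scan due. The patient in that gap has had the combination under study, yet the plan does not require the measurement that defines the primary endpoint.

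The loss is unlikely to be random. The stopping grounds in 6.4 include progression, intercurrent illness and unacceptable adverse events. If patients who stop for those reasons are less likely to be responders, leaving them out raises the ORR. With 15 patients, each one is worth about 7 percentage points (1/15 = 6.7%), and 11.3 intends to set the result beside earlier rates of 13% to 36%. Section 11 does not say how a treated but unassessed patient counts.

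**Working it through.** **1. The plan's own figure.** The exact Clopper-Pearson limits for x responders in n are the 2.5% quantile of Beta(x, n−x+1) and the 97.5% quantile of Beta(x+1, n−x). At n = 15 the widest interval is at 7/15 (equally 8/15): 0.213 to 0.734, width 0.5215. This reproduces the 0.52 in 11.3.

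**2. Timing.** Section 4.4.2: "Pembrolizumab 200 mg will be given every 3 weeks". Infusion k therefore falls at week 3(k−1): infusion 4 at week 9, infusion 5 at week 12. Cycle 5 ends at week 15. Section 4.3.6 places the first quad-shot "prior to cycle 4 (between pembrolizumab cycle 2-3 or 3-4) for all patients".

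| First quad-shot | Infusion at which the 6.6 minimum is met | Reaches infusion 5? |
|---|---|---|
| Between cycles 2 and 3 | 4 (week 9) | Not necessarily |
| Between cycles 3 and 4 | 5 (week 12) | Yes |

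The gap therefore needs the earlier slot and a stop after infusion 4. Footnote f's window runs from cycle 4 to cycle 6, so a scan at cycle 4 is within schedule but not compelled. Sections 4.2 and 7.1 have no such window.

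**3. Effect on the ORR.** Let k be the number of patients who met the minimum and have no post-quad-shot assessment. The documents give no rate for this, so k = 1 or 2 is an assumption. Take 5 responders among those assessed, and compare the reported rate with the rate when the k patients are counted as non-responders.

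| Reading | k | Reported ORR (95% CI) | With the k patients counted (95% CI) | Maximum CI width, as reported |
|---|---|---|---|---|
| Replaced (4.2, 11.3) | 1 | 5/15 = 33.3% (11.8–61.6) | 5/16 = 31.3% (11.0–58.7) | 0.52 |
| Replaced (4.2, 11.3) | 2 | 5/15 = 33.3% (11.8–61.6) | 5/17 = 29.4% (10.3–56.0) | 0.52 |
| Not replaced (6.6, 7.1.1 note) | 1 | 5/14 = 35.7% (12.8–64.9) | 5/15 = 33.3% (11.8–61.6) | 0.54 |
| Not replaced (6.6, 7.1.1 note) | 2 | 5/13 = 38.5% (13.9–68.4) | 5/15 = 33.3% (11.8–61.6) | 0.56 |

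The difference is about 2 to 4 points with replacement (33.3 − 31.3 = 2.0; 33.3 − 29.4 = 3.9) and about 2 to 5 points without (35.7 − 33.3 = 2.4; 38.5 − 33.3 = 5.2).

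**4. Direction.** The reported ORR is too high only if the omitted patients respond less often than the assessed ones. With replacement and k = 2, if one of the two was in fact responding, the rate among all of them would be 6/17 = 35.3%, above the reported 33.3%.

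**The case against.** The strongest case against is that the plan already covers this patient. Four parts of it deserve an answer.

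- **Replacement.** A reader might infer from 6.6 that the patient is simply not replaced, so that the study ends with 13 or 14 evaluable patients and misses its stated precision. The documents do not support that as a settled conclusion. A patient without a response scan has not finished the investigations and is replaced under 4.2, while 11.3 and 11.4 both plan for 15 evaluable. The loss of precision arises only on the 6.6 reading. What stands is that the rules conflict, and that replacement leaves the first patient out of the denominator.
- **Assessment.** A reader might also infer that such a patient can never be assessed. That goes too far. Section 7.1.1 asks for re-evaluation and not for a scan at a set time. Footnote f allows a scan at cycle 4, 7.1.2 refers to routine clinical imaging and allows calipers for superficial lesions, and 6.5 collects later scans. These may recover some patients, but none is required, and recovery would depend on clinical discretion in patients who may be declining.
- **Size.** Exposure is limited to one radiotherapy slot and one stopping point. Section 8.1 quotes 5% permanent discontinuation for adverse reactions, without a time window and without other reasons for stopping, so it does not fix k. It is tempting to say that two losses carry the result past 36%. One loss does not (35.7%), 36% is the pembrolizumab-plus-chemotherapy rate in Table 1, and 11.3 plans no formal test. The shifts lie well inside intervals about 50 points wide. All of this stands and limits the weight of the point.
- **Direction.** Someone who stops for toxicity or by choice may be responding. This also stands: upward bias is plausible but not shown.

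The earlier slot is nevertheless not a corner case. Section 4.3.3 gives it as the slot for all patients, whereas 4.2, 4.3.6 and footnote h allow either. Those passages need reconciling too.

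**Conclusion.** The point holds in limited form. A patient who meets the treatment minimum at infusion 4 and stops has no required post-radiotherapy tumor assessment. If nothing discretionary supplies one, 7.1.1 and 11.3 exclude that patient from the primary ORR, and the plan contradicts itself on replacement.

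For 5 responders and one or two such patients, the effect is about 2 to 4 points if they are replaced and about 2 to 5 if not. The 0.52 width is lost only in the second case. These sizes assume that such patients exist, stay unassessed and are not responding.

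This is not fatal to an estimation pilot, but it affects the only primary endpoint and should be corrected.

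**What to change.** 1. **Scan timing (4.2, 7.1, footnote f; matching wording in 6.2 and 6.5).** Make the already planned first response scan due at a fixed time from the first pembrolizumab dose, for example week 15 ± 3 weeks, where it now falls without delays, or at the end of pembrolizumab if earlier. Apply this to every patient who received a quad-shot, whether or not pembrolizumab continues, and say that one such scan is enough.
2. **Analysis (7.1.1, 11.1, 11.3).** State that a patient who met the 6.6 minimum but has no post-quad-shot assessment counts as a non-responder in the primary ORR.
3. **Replacement (4.2, 6.6, 7.1.1 note, 11.3).** Reconcile these into one rule.

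**Cost.** Wording changes in several sections. No scan is added to the planned number and no extra reader is needed, but the scan must be arranged for the few patients who stop early. The reported ORR may be slightly lower, and the non-responder rule will be too harsh on a patient who stopped while responding. Patients removed before the 6.6 minimum are still replaced and stay outside the ORR; this change does not address them.

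### Section 4.2 replaces any non-completer with no cut-off, in conflict with 6.6 and 7.1.1, so a patient whose response is already scored could be replaced and the denominator of the primary ORR is left open

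*Combined protocol and SAP*

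**What the plan says.** Three places in the protocol decide who fills the 15 slots behind the primary ORR.

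- **Section 4.2 (Study Design):** "If any patient does not complete the study treatment and investigations, the patient will be replaced". Completion is not defined, and neither are the investigations. The same section describes PRO-CTCAE forms at each time point and blood and saliva sampling, including samples around any second or third quad-shot. It also says "Subsequent immunotherapy cycles will be delivered after quad-shot radiotherapy until tumor progression or treatment intolerance" and "The study treatment portion ends for all patients with the last administration of the immunotherapy".
- **Section 6.6 (Criteria for Removal from Study):** replacement applies only to patients removed before "completing at least 2 cycles of ICI followed by at least 1 cycle of quad-shot radiotherapy followed by at least 2 cycles of ICI".
- **Section 7.1.1 (Definitions):** the main definition of evaluable for objective response is "Only those patients who received at least one cycle of quad-shot radiotherapy (given after at least 2 cycles of ICI") and whose target disease has been re-evaluated. A Note then repeats the 6.6 rule: "Note: Per Section 6.6, subjects who are removed from study prior to completing at least 2 cycles of ICI". It does not cite 4.2.

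Section 11.1 reports the percentage with PR or CR and a 95% Clopper-Pearson interval, without naming a population. Section 11.3 requires 15 patients evaluable under 7.1.1 and compares the result with published rates of 13% to 36%.

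**The concern.** The 4.2 rule is wider than the 6.6 rule, and both are current text. A patient past the 6.6 minimum who has a scored scan is kept by 6.6 and 7.1.1. If that patient later withdraws, or misses a questionnaire or a sample around a later quad-shot, the wording of 4.2 calls for replacement.

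This matters because the decision could then be made with the response already known. The ORR is the only primary result, the study has one arm and no formal test, and 11.3 uses the estimate to judge whether further study is warranted. A denominator that depends on which section is followed weakens that estimate, even in a pilot.

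**Working it through.** **1. The plan's own figure.** The exact 95% interval for 7/15 runs from 0.2127 to 0.7341, a width of 0.5215. This reproduces the 0.52 in 11.3, so the stated precision is correct.

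**2. When the 6.6 minimum is reached.** Sections 4.2 and 4.3.6 and calendar note h in 6.1 place the first quad-shot between cycles 2-3 or 3-4.
- Quad-shot between cycles 2-3: the two later infusions are cycles 3 and 4, so the minimum is met at cycle 4.
- Quad-shot between cycles 3-4: the two later infusions are cycles 4 and 5, so the minimum is met at cycle 5.

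Section 7.1 puts the first restaging after 5 cycles. A patient scored on schedule has therefore passed the 6.6 minimum and is kept by 6.6 and 7.1.1.

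**3. What 4.2 can still reach after that scan.** Routine correlative samples are due before the first five infusions and the first quad-shot, so they are normally finished. What remains is PRO-CTCAE at later cycles, samples around an optional second or third quad-shot, and withdrawal. Each can leave a scored patient short of completion under 4.2.

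**4. The narrower overlap between 6.6 and 7.1.1.** Calendar note f in 6.1 allows scans every 5 cycles ± 1. Take a quad-shot between cycles 3-4 and a scan after cycle 4 that shows PD. The patient has had one infusion since the quad-shot. The main definition in 7.1.1 is met. If the patient is then removed for PD, 6.6 replaces them, because fewer than two later cycles were given. An unscheduled early scan has the same effect. Section 4.3.3 mentions only the 2-3 interval for the first quad-shot, an inconsistency that also needs reconciling. On that text alone, the overlap would need an unscheduled scan before cycle 4.

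**5. Size.** One patient is 1/15 = 6.7 points. The documents do not say how many scored patients would be replaced, so the number k is an assumption. With 5 responders and k scored non-responders replaced and dropped, the reported rate is 5/15; keeping everyone gives 5/(15 + k).

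| k | Reported | All scored patients kept |
|---|---|---|
| 1 | 5/15 = 33.3% (11.8 to 61.6) | 5/16 = 31.3% (11.0 to 58.7) |
| 3 | 5/15 = 33.3% | 5/18 = 27.8% (9.7 to 53.5) |
| 5 | 5/15 = 33.3% | 5/20 = 25.0% (8.7 to 49.1) |

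The direction depends on who is dropped. With 16 scored patients and 5 responders (31.3%), dropping one non-responder gives 5/15 = 33.3%; dropping one responder gives 4/15 = 26.7%.

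**The case against.** The strongest defence is that the denominator is already anchored. Section 11.3 points to 7.1.1, 7.1.1 points to 6.6, and neither cites 4.2. A reader might infer from 4.2 that recorded responses will be discarded. The text says only that the patient is replaced. If scored responses are kept, replacement only adds patients and the table above does not apply. This objection stands against any claim of a plan to drop data. It does not settle the matter, because no section says that the response is kept or that 4.2 gives way.

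A reader might also infer that patients who stop for toxicity are replaced. Section 4.2 gives pembrolizumab "until tumor progression or treatment intolerance", so stopping for either reason can be read as the planned end of treatment. The heading of 6.2 separates completed treatment from discontinuation for toxicity, so the text is unclear, but it does not establish that reading. Nor does the 35% grade 2 mucositis/xerostomia in Table 2 show that missed saliva samples would be common here. It is a combined figure from a series given concurrent carboplatin or cetuximab, and 4.4.7.3 excludes concurrent chemotherapy. Nothing in the documents links missed samples to non-response.

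On the narrower overlap, the Note in 7.1.1 can be read as an exception to the main definition, which makes replacement a design choice. That is fair. The choice still takes a documented non-responder out of the count, and the text does not say whether that PD is reported.

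Finally, the shifts shown are small against an interval up to 0.52 wide, and 28% and 33% both lie within 13% to 36%. That limits the practical effect but does not resolve the conflict.

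**Conclusion.** The conflict holds. Section 4.2 has a replacement rule with no cut-off, 6.6 and the 7.1.1 Note have one with a cut-off, and no text ranks them or says what happens to a replaced patient's recorded response. As written, 4.2 can reach a patient already scored. Within the protocol's own windows, 6.6 can replace a patient with documented PD who meets the main definition in 7.1.1.

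A reader might infer that the ORR will be biased upward. The documents do not support that for 4.2: they give neither the size nor the direction. What can be said is that each swap moves the rate by up to 6.7 points. The 33% against 28% comparison assumes 5 responders, 3 scored non-responders replaced, and their responses dropped. In the narrower overlap the replaced patient is a non-responder, so excluding that patient could only raise or leave unchanged the ORR.

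This should be corrected before analysis. It is not an error in the sample size or in the stated precision.

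**What to change.** Replace the sentence in 4.2 with: *Replacement follows Section 6.6 only.* Add to 6.6 and 7.1.1: *A patient with a response assessment after the quad-shot is not replaced and stays in the ORR denominator, whatever later treatment, sample or questionnaire is missed.*

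The cost is one sentence replaced and one sentence added in two places. It needs no new data and changes no treatment rule; fewer replacements would be needed. The target of 15 evaluable patients and the 0.52 maximum interval width are unchanged. The downside is that a few early-progressing patients with less than the 6.6 minimum exposure will count, so the ORR may be slightly lower.
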